In addition, data will be collected to ascertain non-major clinically relevant bleeding, defined as overt bleeding not meeting the criteria for major bleeding, but associated with medical intervention, unscheduled contact (visit or telephone call) with a physician, (temporary) cessation of study treatment, or associated with discomfort for the subject such as pain or impairment of activities of daily life, and other bleeding, defined as any other overt bleeding that does not meet the ISTH criteria for major or non-major clinically relevant bleeding (Section 9.5).

All serious adverse events except the study outcomes (VTE-related death, MI, acute coronary syndrome [ACS], stroke, transient ischemic attack [TIA], symptomatic VTE [lower or upper extremity DVT and PE], bleeding events) will be collected. Refer to Section 12.3.1, All Adverse Events for more details.

Interim Analysis

The primary reason for the prespecified interim analysis is to assess for futility.

Pharmacokinetics Analysis

The PK analysis will be done:

- To predict the overall exposure of rivaroxaban and estimate the PK model parameters for medically ill patients.
- To describe the effect of dosing modification on exposure for subjects with $\text{CrCl} \geq 30$ mL/min and < 50 mL/min.

Medical Resource Utilization and Health Economics

The medical resource utilization and health economics will assess cost drivers and details on medical resource utilization and health economics can be found in Section 9.4.

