9.5. Safety Evaluations and Outcomes

9.5.1. Bleeding Events

The study will include the following evaluations of safety and tolerability according to the time points provided in the [TIME AND EVENTS SCHEDULE](#): ISTH major bleeding, non-major clinically relevant bleeding, other bleeding, adverse events, and clinical laboratory tests.

The study will use the ISTH Bleeding Event Classification Scale to assess bleeding events as major, non-major clinically relevant bleeding, or other bleeding. Similar to efficacy outcomes, the same independent CEC will adjudicate and classify bleeding events according to definitions in the CEC charter. The CEC will also classify bleeding events using the Bleeding Academic Research Consortium scale as a supportive approach.²⁷

The principal safety outcome for this study is major bleeding using validated ISTH bleeding criteria. Other safety outcomes are non-major clinically relevant bleeding and other bleeding.

An ISTH major bleeding event is defined as overt bleeding that is associated with:

- A fall in hemoglobin of 2 g/dL or more, or
- A transfusion of 2 or more units of packed red blood cells or whole blood, or
- A critical site: intracranial, intraspinal, intraocular, pericardial, intra-articular, intramuscular with compartment syndrome, retroperitoneal, or
- A fatal outcome

Non-major clinically relevant bleeding is defined as overt bleeding not meeting the criteria for major bleeding but associated with medical intervention, unscheduled contact (visit or telephone call) with a physician, (temporary) cessation of study treatment, or associated with discomfort for the subject such as pain or impairment of activities of daily life.

Examples of non-major clinically relevant bleeding are:

- Epistaxis if it lasts for more than 5 minutes, if it is repetitive (ie, 2 or more episodes of true bleeding, ie, not spots on a handkerchief, within 24 hours), or leads to an intervention (packing, electrocautery, etc.)
- Gingival bleeding if it occurs spontaneously (ie, unrelated to tooth brushing or eating), or if it lasts for more than 5 minutes
- Hematuria if it is macroscopic, and either spontaneous or lasts for more than 24 hours after instrumentation (eg, catheter placement or surgery) of the urogenital tract
- Macroscopic gastrointestinal hemorrhage: at least 1 episode of melena or hematemesis, if clinically apparent
- Rectal blood loss, if more than a few spots
- Hemoptysis, if more than a few speckles in the sputum, or

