12.3. Procedures

12.3.1. All Adverse Events

In this study, recording of only a subset of adverse events is necessary. However, any adverse event of particular concern to the investigator may be recorded in the eCRF to alert the sponsor.

The following are excluded from adverse event collection and reporting, regardless of seriousness or severity. Exempted events will be captured on the eCRF as suspected outcome events only and will be waived from unblinding and exempted from expedited reporting and include:

- VTE-related death (death due to PE or death in which PE cannot be ruled out as the cause)
- MI
- ACS
- Stroke
- TIA
- Symptomatic VTE (lower or upper extremity DVT and PE)
- Bleeding events

If the CEC determines that a suspected event does not meet the criteria for an outcome event as defined in the CEC charter, it will still be excluded from adverse event collection and reporting even if serious criteria were met.

Serious Adverse Events

All serious adverse events that are not outcome events as listed above should be reported to the sponsor as described in Section 12.3.2. While one of the efficacy outcome measures is ACM, any non-VTE-related death will be reported to the sponsor as a serious adverse event.

Certain adverse events are considered to be Adverse Events of Special Interest and should be reported as serious adverse events. These include:

- Suspected severe toxic effect on the bone marrow, such as severe thrombocytopenia (platelet count less than 50,000/ μ L), severe neutropenia (white blood cell count less than 500/ μ L), pancytopenia, aplastic anemia
- Suspected severe hypersensitivity reaction (eg, anaphylaxis, angioedema, severe urticaria, bronchospasm, etc.)
- Severe skin reactions such as Stevens-Johnson Syndrome
- Suspected severe liver injury

Non-Serious Adverse Events

The following should be reported:

- Non-serious adverse events leading to permanent study drug discontinuation
- All severe non-serious adverse events (regardless of relation to study drug) including severe laboratory abnormalities will be collected except the study outcomes.

Any other non-serious adverse events do not require reporting. However, any adverse event of particular concern to the investigator may be recorded in the eCRF to alert the sponsor.

Reporting Timelines and Processes

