Attachment 1: Efficacy Outcomes

All efficacy evaluations and outcomes described in Section 9.2 will be evaluated and adjudicated by the CEC (defined below). Safety outcomes are defined in Section 9.5.

1. Death will be assigned to 1 of the following:
 - a. CV death
 - i) VTE-related
 - (1) VTE-related death – death due to confirmed PE documented by objective testing or autopsy,
 - (2) VTE-related, PE cannot be ruled out – death, which cannot be attributed to a documented cause and for which pulmonary embolism cannot be ruled out (unexplained death)
 - ii) Other CV death
 - b. Non-CV death – death not included in 1 of the above categories
2. Symptomatic DVT – displaying signs or symptoms of proximal or distal lower extremity DVT, upper extremity DVT, or other DVT and confirmed by adjudication, based on 1 or more of the following diagnostic criteria:
 - a. a non-compressible venous segment on compression ultrasonography, or in patients with a history of previous DVT, either a new non-compressible venous segment or a substantial increase (4 mm or more) in the diameter of the vein during full compression in a previously abnormal segment on ultrasonography, or
 - b. the presence of an intraluminal filling defect on venography, or
 - c. DVT documented at autopsy.

If in patients with history of previous DVT or incomplete documentation of the previous episode is available, additional criteria may be integrated into the adjudication of the current event, such as: ultrasonography appearance of the thrombus, or D-dimer at presentation. Soleal or muscular branch DVTs, lower extremity superficial DVT will not be included. The totality of available clinical, imaging and laboratory findings should be considered

3. Symptomatic PE – displaying signs or symptoms suggestive of PE and confirmed by adjudication based on 1 or more of the following diagnostic criteria:
 - a. an intraluminal filling defect on computed tomography (CT) angiography or spiral CT, or
 - b. an intraluminal filling defect on pulmonary angiography or cutoff of a vessel more than 2.5 mm in diameter, or
 - c. a perfusion lung scan defect of at least 75% of a segment with corresponding normal ventilation (high probability ventilation-perfusion (V-Q) scan), or
 - d. a non-high probability V-Q scan abnormality associated with DVT documented by ultrasonography or venography, or

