6.2. Adverse Events

For the purposes of this study (and after discussion with appropriate regulatory agencies) a value-driven approach to safety data collection will be utilized. Certain non-serious adverse events will not be collected, while certain events will be collected as outcome and therefore not reported as serious adverse events. All data on safety and outcomes will be reviewed regularly by an unblinded IDMC. For AEs that are collected, the verbatim terms reported in the eCRF by investigators to identify adverse events will be coded using the Medical Dictionary for Regulatory Activities (MedDRA).

Treatment-emergent adverse events (TEAE) are defined as those adverse events that start between the first study drug and the last study drug + 2 days.

Summary of the following adverse events will be provided by treatment group:

- Post-baseline (on or after the first study drug) adverse events
- Treatment-emergent adverse events
- Adverse events with onset > 2 days from the stop of study drug
- Post-baseline serious adverse events
- Treatment-emergent serious adverse events (TESAE)
- Serious adverse events with onset > 2 days from the stop of study drug
- Adverse events leading to permanent study drug discontinuation
- Adverse events with outcome of death

In addition, incidences of some of the above adverse events by system organ class and dictionary-derived (preferred) term will be provided.

Additional summaries, listings, or subject narratives may be provided, as appropriate.

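### Protocol 12.3.1 both exempts fatal bleeding, fatal MI and fatal stroke from SAE reporting and requires them as SAEs, so 24-hour notice and the SAP's AE-death table depend on which sentence a site follows

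*Protocol*

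**What the plan says.** Protocol 12.3.1 opens its exemption with "The following are excluded from adverse event collection and reporting, regardless of seriousness or severity". The list beneath names VTE-related death, MI, ACS, stroke, TIA, symptomatic VTE and "Bleeding events". VTE-related death is the only death named, but MI, stroke and bleeding are not limited to non-fatal events. On handling, the section adds: "Exempted events will be captured on the eCRF as suspected outcome events only and will be waived from unblinding and exempted from expedited reporting".

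Under its serious adverse event subheading, the section sends to the sponsor only those SAEs that are not listed outcomes. The next sentence, which mentions that all-cause mortality is an efficacy measure, says that "any non-VTE-related death will be reported to the sponsor as a serious adverse event".

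Three other places bear on the exemption, and none makes an exception for death:

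- Protocol 3.2 (Choice of Safety Measures) states the SAE collection rule as "All serious adverse events except the study outcomes (VTE-related death, MI, acute coronary syndrome [ACS], stroke, transient ischemic attack [TIA" and continues to symptomatic VTE and bleeding events.
- Protocol 12.1.1 says that efficacy and safety outcomes do not count as adverse events or SAEs in this study.
- SAP 6.2 says that certain events are collected as outcomes and so are not reported as SAEs. It then lists among its summaries by treatment group "Adverse events with outcome of death".

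**The concern.** Bleeding is the harm that defeated the earlier extended-prophylaxis trials described in Protocol 1.1.5, and Protocol 1.1 presents this design as an attempt to reduce it. The handling of a fatal bleed should therefore not be left to interpretation. A site that relies on the exemption records the death on the outcome pages. A site that relies on the death sentence files an SAE within 24 hours. Each can point to text in the same section.

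Two things are at stake. The first is how quickly the sponsor learns of these deaths. The second is the meaning of the SAP 6.2 death summary, which is filled from collected adverse events. If sites differ in their reading, it will hold some deaths from these three causes and omit others. Sites are blinded, so the choice of route should not depend on arm. But if fatal bleeding is more frequent in one arm, omissions would not cancel between arms.

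**Working it through.** The plan states no figure on this point, so the check is textual: take each kind of death and apply both rules.

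**Do the three causes fall inside the exemption?** For bleeding, yes: Protocol 9.5.1 lists "A fatal outcome" among the ISTH major bleeding criteria, so a fatal bleed is itself a study outcome and a bleeding event on the list. For MI and stroke, the list names the event without qualification, and SAP 5.5.1 defines fatal MI and fatal stroke as recognised categories. The exemption's opening words rule out reading seriousness as a limit.

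**Do they fall inside the death sentence?** Yes, when the death is not VTE-related. Attachment 1 divides VTE-related death into death from confirmed PE and "death, which cannot be attributed to a documented cause and for which pulmonary embolism cannot be ruled out". A death attributed to a documented bleed, MI or stroke is neither.

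| Kind of death | Exemption list | Death sentence | Result |
|---|---|---|---|
| PE, or PE not ruled out | Exempt by name | Does not apply | Consistent: outcome route |
| Cause not on the list (for example, infection) | Not exempt | SAE | Consistent: SAE route |
| Fatal bleeding | Exempt | SAE | Contradictory |
| Fatal MI | Exempt | SAE | Contradictory |
| Fatal stroke | Exempt | SAE | Contradictory |

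**Is precedence stated?** No. Nothing in 12.3.1 ranks the two rules, and Protocol 3.2 and 12.1.1 and SAP 6.2 restate the exemption in general terms.

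**What changes with the route?**

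- *Timing.* Protocol 12.3.2 puts a 24-hour limit on SAEs. For the eCRF, Protocol 17.5 asks for completion as soon as possible after a visit, with transmission in a period agreed between sponsor and site. Neither document sets a 24-hour limit for outcome pages.
- *SAP 6.2 death summary.* If every site follows the exemption, it contains no fatal bleed, fatal MI or fatal stroke. If every site follows the death sentence, it contains all of them. With mixed practice it contains an unknown part.

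**What does not change?** Protocol 9.2.1 requires every death to be submitted for adjudication, and 9.5.1 requires the same of every suspected bleed. All-cause mortality (SAP 5.3), ISTH major bleeding (SAP 6.1) and the benefit-risk comparisons, which name fatal bleeding, fatal MI and fatal ischemic stroke (SAP 7), rest on adjudicated events. None needs an SAE form.

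**The case against.** The strongest reply is that the death sentence is a specific rule meant to override a general list. VTE-related death is the only death on the list, the sentence deals with deaths expressly, and the adjudication list in Protocol 3.3.3 puts death beside non-fatal MI and non-fatal stroke as separate items. This reading is plausible and may be what was intended. It is not stated, however. It runs against the exemption's opening words, the restriction to outcome capture only, and Protocol 12.1.1.

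The second reply is that little is lost, because the CEC sees every death and, under Protocol section 12, an unblinded data monitoring committee regularly reviews all safety and outcome data. That stands, and it limits the point to sponsor notice and one descriptive summary. The eCRF guidelines or the CEC charter, which are not available here, may also set a faster timeline for outcome pages.

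Three stronger readings are tempting but not supported:

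- *That unexplained deaths have the same conflict.* The list exempts deaths in which PE cannot be ruled out. A further sentence in 12.3.1 keeps a suspected event outside adverse event reporting even if the CEC later decides that it is not an outcome. That largely settles the matter.
- *That the number of affected deaths can be obtained from an assumed mortality rate.* Such a figure would count all deaths, including those with one clear route. The documents give neither a mortality rate nor a split by cause.
- *That no table of deaths to Day 75 is planned.* SAP section 1 places all output titles and layouts in a separate specification, and SAP 6.2 allows additional summaries, so this cannot be established.

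**Conclusion.** The inconsistency is real and confined to fatal bleeding, fatal MI and fatal stroke. For these deaths, 24-hour notice to the sponsor and inclusion in the SAP 6.2 summary depend on which sentence a site follows. That summary cannot be interpreted as a count of fatal events until the rule is settled. The primary, mortality, major bleeding and benefit-risk results are not at risk.

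No number of deaths is attached. The conclusion rests on the text alone, and on two assumptions: that no site instruction outside these documents gives precedence or a 24-hour limit for outcome pages, and that the SAP 6.2 summary is filled from collected adverse events, as its placement implies. If an outside instruction resolves the point, what remains is a wording correction.

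**What to change.** Reconcile Protocol 3.2, 12.1.1 and 12.3.1 and SAP 6.2 into one rule that says whether fatal bleeding, fatal MI and fatal stroke are reported as SAEs on the 24-hour route. Editing 12.3.1 alone would leave the blanket exemptions in 3.2 and 12.1.1 standing. Whichever rule is chosen, state explicitly whether these deaths keep the waiver from unblinding and expedited reporting. VTE-related deaths are already handled consistently and need no new rule.

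In SAP 6.2, build the death summary from CEC-adjudicated deaths by cause and arm, with the time window stated, so that it does not depend on the route a site used. The death classes in Attachment 1 have no separate line for bleeding, MI or stroke. Fatal bleeding would come from the bleeding adjudication, and fatal MI and fatal stroke from the SAP 5.5.1 definition. If the adverse-event version is kept as well, a footnote should say which outcome deaths it excludes.

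The cost is a wording amendment in four places and either a few extra notifications or one revised table. No new data are needed, because all deaths already go to the CEC.

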9.5.3. Other Safety Assessments

Adverse Events

Adverse events will be reported by the subject (or, when appropriate, by a caregiver, surrogate, or the subject's legally acceptable representative) for the duration of the study. Adverse events will be followed by the investigator as specified in Section 12, Adverse Event Reporting.

Clinical Laboratory Tests

Separate laboratory screening tests are not expected to be performed by the investigator as these will likely be part of the subjects' hospital evaluation. No pre-specified laboratory tests will be performed for the duration of the study. However, these subjects are likely to have local laboratory tests performed during their index hospitalization. Any laboratory test along with reference ranges relevant to a serious adverse event or an outcome event should be recorded on the appropriate eCRF page.

The following tests results with reference ranges will be obtained from the hospital laboratory/local laboratory at the time of the index hospitalization:

- hematology
 - hemoglobin
 - platelet count
- serum creatinine (CrCl to be calculated by IWRS using Cockcroft-Gault formula⁶)
- D-dimer
- serum or urine pregnancy testing for women of childbearing potential only

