12.3.2. Serious Adverse Events

All serious adverse events occurring during the study must be reported to the appropriate sponsor contact person by study-site personnel within 24 hours of their knowledge of the event.

Information regarding serious adverse events will be transmitted to the sponsor using the Serious Adverse Event Form, which must be completed and signed by a physician from the study site, and transmitted to the sponsor within 24 hours. The initial and follow-up reports of a serious adverse event should be made by facsimile (fax, e-mail).

All serious adverse events that have not resolved by the end of the study, or that have not resolved upon discontinuation of the subject's participation in the study, must be followed until any of the following occurs:

- The event resolves
- The event stabilizes
- The event returns to baseline, if a baseline value/status is available
- The event can be attributed to agents other than the study drug or to factors unrelated to study conduct
- It becomes unlikely that any additional information can be obtained (subject or health care practitioner refusal to provide additional information, lost to follow-up after demonstration of due diligence with follow-up efforts)

Any event requiring hospitalization (or prolongation of hospitalization) that occurs during the course of a subject's participation in a clinical study must be reported as a serious adverse event, except hospitalizations for the following:

- Social reasons in the absence of an adverse event
- Surgery or procedure planned before entry into the study (must be documented in the eCRF).

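### Protocol 12.3.1 names severe neutropenia as an example of a special-interest event but measures it by total white cells, so the printed cut-off is narrower than the condition it names

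*Protocol*

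**What the plan says.** Protocol 12.3.1 (All Adverse Events) limits which adverse events are recorded and then sets out a short list that must go through the serious route: "Certain adverse events are considered to be Adverse Events of Special Interest and should be reported as serious adverse events". The first entry is "Suspected severe toxic effect on the bone marrow, such as severe thrombocytopenia", with a platelet count below 50,000/µL in parentheses. It continues with "severe neutropenia (white blood cell count less than 500"/µL and ends with "pancytopenia, aplastic anemia", which carry no number.

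The consequence of serious status is in Protocol 12.3.2: such events "must be reported to the appropriate sponsor contact person by study-site personnel within 24 hours of their knowledge of the event".

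Three other provisions bear on the point:

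- Protocol 12.3.1 also states: "All severe non-serious adverse events (regardless of relation to study drug) including severe laboratory abnormalities will be collected except the study outcomes".
- Protocol 12.3.2 states: "Any event requiring hospitalization (or prolongation of hospitalization) that occurs during the course of a subject's participation in a clinical study must be reported" as serious, with two exceptions (social reasons, and procedures planned before entry).
- Protocol 9.5.3 states: "No pre-specified laboratory tests will be performed for the duration of the study".

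Neither the protocol nor the SAP gives an absolute neutrophil count anywhere. The SAP does not mention neutropenia.

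**The concern.** The condition and the measurement refer to different cells. In the neighbouring example, thrombocytopenia is measured by platelets, so label and count agree. In the neutropenia example they do not.

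The direction of the mismatch is fixed. A total white cell count can never be lower than the neutrophil count, so the printed cut-off can only leave out cases that the same figure applied to neutrophils would include. It cannot add any.

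What is at stake is the speed and class of reporting for a possible marrow-toxicity signal. The protocol collects adverse events selectively, so the explicit special-interest list tells sites what must not be missed. Where a number is printed, some sites will apply it as a rule.

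**Working it through.** **Inputs from the documents.** The named condition is severe neutropenia. The printed measure is total white cells below 500/µL. Both are in Protocol 12.3.1. No sample size, power or alpha figure is involved.

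**Step 1: relation between the two counts.** Let W be total white cells, N neutrophils and O all other white cells, each per µL. Then W = N + O, with O ≥ 0.

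- If W < 500, then N ≤ W < 500. Every case that meets the printed number has neutrophils below 500.
- If N < 500, the printed number is met only when N < 500 − O. Otherwise it is not met.

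So the printed set is contained in the set defined by N < 500, and is strictly smaller whenever O is above zero.

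**Step 2: one illustration (assumed values).** Take W = 1,200/µL with 25% neutrophils. Then N = 1,200 × 0.25 = 300/µL, which is below 500. But W is 1,200 / 500 = 2.4 times the printed cut-off, so the printed number is not met.

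**Step 3: white cell count that corresponds to 500 neutrophils (assumed differential).** The documents give no differential. If neutrophils are 25% to 60% of white cells:

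- at 60%: 500 / 0.60 = 833 white cells/µL
- at 25%: 500 / 0.25 = 2,000 white cells/µL

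Both lie above 500.

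**Step 4: how far the missed share can range.** Assume O is fixed and N is spread evenly over 0 to 500. The share of cases with N < 500 that do not meet W < 500 is then O / 500, capped at 100%.

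| Other white cells O (per µL) | Printed number met only if N is below | Share missed |
|---|---|---|
| 0 | 500 | 0% |
| 50 | 450 | 10% |
| 100 | 400 | 20% |
| 250 | 250 | 50% |
| 400 | 100 | 80% |
| 500 or more | cannot be met | 100% |

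The last row holds whatever the distribution of N. The other rows depend on the even spread. Because the result runs from 0% to 100% with an input that the documents do not supply, no single share can be stated.

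**Step 5: routes open to a case that the printed number leaves out.** Take N below 500 and W above 500.

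1. If the investigator suspects severe marrow toxicity, the case falls in the parent category of 12.3.1 and is reported as serious.
2. If it is life-threatening, requires or prolongs hospitalization, or is medically important, it is serious under Protocol 12.1.1. For hospitalization, 12.3.2 says so again.
3. If neither applies but it is graded severe, 12.3.1 collects it as a severe non-serious event.
4. If it leads to permanent discontinuation of study drug, 12.3.1 collects it as a non-serious event.

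Routes 1 and 2 keep the 24-hour report. Routes 3 and 4 keep the record but not the 24-hour report.

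**The case against.** The strongest reply is that the number is not the trigger. The special-interest event is a suspected severe toxic effect on the marrow. The cytopenias are examples of it, and two of them have no threshold at all. An investigator who sees a neutrophil count of 300/µL and suspects the marrow should report it whatever the total white cell count. This stands, and it limits the point to sites that treat the parenthesis as the rule.

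The ordinary seriousness criteria also stand as an independent route. A reader might infer that a missed case could reach the sponsor only as a non-serious event. Sections 12.1.1 and 12.3.2 do not support that. The severe non-serious route gives further cover, but it depends on grading: Protocol 12.1.3 describes severe in terms of distress and loss of function and leaves laboratory findings to clinical judgment.

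A reader might also infer that most severe neutropenia escapes the rule. The documents do not support this either. It needs an assumed white cell differential and a reading of the example as the whole gate.

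Nor do they support the claim that a special-interest count by arm would be biased. Neither Protocol 11.6 nor SAP 6.2 specifies such a table. Any effect would fall on the serious adverse event summaries in SAP 6.2.

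Finally, on-study blood counts come only from local care, so few cases would surface under either wording.

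None of these replies makes the term and the count agree.

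**Conclusion.** The point holds as a definitional inconsistency in current, operative text. The cell type measured does not match the condition named, and read literally the example is narrower than its name. That conclusion needs no assumption beyond neutrophils being a subset of white cells.

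The practical loss is confined to a 24-hour serious report for a case with neutrophils below 500/µL and white cells above 500/µL that is not reported as suspected marrow toxicity and meets no ordinary seriousness criterion. The number of such cases cannot be derived from the documents and is likely small. The primary outcome, the principal safety outcome, power and alpha are untouched. This is a minor point, worth correcting because the correction is cheap.

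**What to change.** The sponsor should reconcile the term and the count in Protocol 12.3.1 so that the cell type measured is the one the condition names, and notify sites. The documents show that the two disagree, not which was intended, so the sponsor must confirm this first. If neutrophils were meant, the smallest edit names the neutrophil count and keeps the printed figure. The SAP needs no change.

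The cost is a few words in the protocol and a site notice, with possibly a few more expedited reports.
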